### **Psychometric properties for non-investigator derived measures:**

SCID Interview for BED: The SCID's severity scales demonstrated substantial internal consistency (all Cronbach's alphas  $>.80$ ), test-retest reliability, concurrent, and predictive validity.

PHQ-9: The internal consistency reliability (Cronbach's alpha 0.89) and inter-rater reliability (intra class correlation coefficient, 0.94; 95% CI, 0.86-0.95) were high. PHQ-9 has good reliability and at cut off score  $\geq 9$ , it has good validity to identify depression in primary care. Similarly, the PHQ-8, similar to PHQ-9 (with the omission of one question) is as useful as the PHQ-9 with strong validity and reliability

Social Problem-Solving Inventory-Revised: The internal consistency reliability (Cronbach's  $\alpha$  0.95) was high. The SPSI-R score was significantly associated ( $p < .05$ ) with various subscales from calories, exercise, distress, and quality of life suggesting concurrent validity.

The User Engagement Scale Short Form (UES-SF): The UES-SF has shown to be statistically reliable ( $\omega = 0.88$ ). Furthermore, each subscale highly correlates with the remaining items in the scale. This suggested that each subscale was suitable to accurately represent the value of the overall components from which the subscales were derived. Accordingly, these items were defined to be the UES-SF and were taken forward for evaluation.

[If applicable, describe the use of audiotape and/or videotape, provide justification for use and indicate if this is a requirement of participation.]

The recording feature on WebEx webinars will be used for recording audio for the end-of-study focus groups. The recorded audio is necessary in order to turn the information said by participants into a transcript for analysis. This grant has an iterative process. The information we receive from participant's feedback through the focus group help to inform the future phases of this study. The recordings are deleted once the transcription is finished. The transcription is anonymous and their names, if spoken during the call, are replaced with their REDCap ID number. We ask them to only say their first name if there are multiple people on the call in order to decipher who is saying what. If they are uncomfortable with using their name, we will provide an alias. During the initial screening, we will ask if they are comfortable being audio-recorded during a focus group call. If they select no, they will be excluded from the study. More information about the privacy/confidentiality of the recordings will be provided in the applicable section.

[If the study involves use of *deception* or *incomplete disclosure*, explain the reason why this is necessary to answer the research question(s). Complete the alteration of consent section below]

N/A

[Describe opportunities provided to participants to ask questions in order for them to make an informed decision regarding participation.]

Participants are able to ask questions during the telephone screening and the webinar. They may also email the study team at any time.

**Data Analysis:** [For all studies, specify the analytic techniques the researcher will use to answer the study questions. Indicate the statistical procedures (e.g. specific descriptive or inferential tests) that will

be used and why the procedures are appropriate. For qualitative data, specify the proposed analytic approaches.]

Proportion of participants meeting app use, engagement, acceptability, and burden targets will be calculated. We will summarize burden ratings as mean (SD). We will conduct thematic analyses of interview data regarding likes/dislikes for each feature and the overall program. Drs [name] and [name] will develop a codebook based on themes emerging during an initial review. The team will finalize themes before final independent coding and consensus. We will calculate inter-rater reliability and will reach consensus via discussion. We will summarize frequency of themes. We will use NVivo 12 (QSR International, Melbourne, Australia) to manage and analyze qualitative data and SAS 9.4 (SAS Institute Inc., Cary, NC) to analyze quantitative data.

**Inclusion/Exclusion Criteria:** [List ALL inclusion and exclusion criteria. Any proposed exclusion criterion based on gender (women of childbearing potential), age, or race must include justification for the exclusion.]

#### **Inclusion Criteria**

- 18-65 years old;
- BMI 27-45 kg/m^2;
- Wi-Fi connectivity at home (for Wi-Fi scale);
- Logs into Facebook at least 5 days per week over the past 2 weeks;
- Has posted/replied on Facebook at least twice a week in the past 2 weeks;
- Able to participate in the study in English; and
- Interested in losing weight

Age justification: Children under 18 require different programming for weight loss and maintenance given their developmental needs. Weight loss is often not indicated for elderly adults and should be medically supervised.

#### **Exclusion Criteria**

- Under the age of 18 and over the age of 65;
- BMI under 27 or over 45 at screening; then under 25 at the point of the first Fitbit Aria weight;
- Does not have Wi-Fi connectivity at home;
- Does not have a Facebook account;
- Does not log into Facebook at least 5 days per week over the past 2 weeks;
- Did not post/reply on Facebook twice a week over the past 2 weeks;
- Not able to participate in the study in English;
- Does not live in the United States;
- Pregnant/lactating or plans to become pregnant during study period;
- Bipolar disorder, substance abuse, psychosis, bulimia, binge eating disorder, or severe depression;
- Had bariatric surgery or plans to have surgery during the study;
- Currently taking medication affecting weight;
- Chronic pain that interferes with the ability to exercise;
- Type 1 Diabetes;
- Type 2 Diabetes;
- Unable to make dietary changes or increase physical activity;
- Unable to walk ¼ mile unaided without stopping;
- Currently smokes or vapes nicotine;

- No phone connectivity at home and work;
- Has a condition that precludes dietary changes (i.e. ulcerative colitis, Crohn's disease, active diverticulitis, renal disease);
- Meets criteria for severe depression on the PHQ-8 (score of >19) ;
- Not interested in losing weight;
- Does not currently own a smartphone;
- Smartphone type and/or version not meeting app requirements;
- Participated in previous weight loss studies under the PI;
- Unable to attend the orientation webinar;
- Did not complete baseline survey;
- Has concerns about being in a Facebook group with other UConn faculty, staff, and students;
- Had major surgery in past 6 months;
- Has an implanted cardiac defibrillator or pacemaker
- Did not complete screening and on-board processes of study;
- Not willing to be audiotaped for focus groups;
- Prisoner; or
- Unable to provide consent

[Describe the conditions under which participants may be removed from the study, i.e., noncompliance with study rules, study termination, etc.]

Participants will be withdrawn from the study if: they choose to drop from participation, do not complete all screening/on-boarding procedures, post inappropriate content on the social network, or post inappropriate content during peer mentoring. Participants reporting that they would like to withdraw from the study will be given the option to: 1) withdraw from all intervention-related activity and contacts, but still complete the final assessment or 2) withdraw from the study completely with no additional study contact. If a participant becomes pregnant during the study, they will be withdrawn from the intervention, but will be given the option still complete the follow-up assessments.

**Potential Harms/Risks and Inconveniences:** [Describe the potential risks to participants (and secondary participants, if applicable) and *steps taken to minimize risks* for each participant population. Assess the likelihood of the risk occurring and, if it were to occur, the seriousness to the participant. Types of risks to consider include, but are not limited to: physical, psychological, social, legal, employment, and financial.]

Possible risks for being in this study includes: Injury while exercising during the intervention, breach of confidential information during the intervention or focus group, and discomfort completing measures during the intervention or assessments, or using the app during the intervention. The attempt to avoid risks to participants will be addressed by: suggesting moderate intensity exercise to avoid discomfort, pain, or injury. Participants reporting discomfort will be referred to their PCP. Injuries are unlikely to occur since we screen out medical conditions that could make someone prone to injury and we only suggest moderate activity. Moderate-level physical activity is 3.0 - <6.0 METs, which includes activities such as brisk walk at 2.5-4 mph, bicycling, gardening, dancing, water aerobics, canoeing, playing doubles tennis. etc.). If participants were to be injured, the likelihood that the injury would be serious is also rare and unlikely. We also provide participants with information on exertion level and remind them to see medical attention if there is pain. Tracking data for the screening, intervention, follow-ups, and focus groups will be stored electronically in REDCap, a network secure data entry program;

electronic data being collected from the app will be transmitted to WPI will be encrypted. During the focus groups participant may not keep what others say confidential. At the start of the group, we will remind participants that they may skip anything that they do not want to answer.

Additionally, participants will be given the option to complete an individual interview in place of a focus group if they prefer more privacy. Participants will be informed that they may withdraw from the study at any time if they feel discomfort with any of the study procedures. We will use Otter.ai transcription software to produce transcripts. Otter.ai will not have access to identified data and will retain no ownership rights to the recordings or transcripts. Any privacy-related problems will be brought to the attention of the PI immediately.

[Describe any anticipated inconveniences the participants may experience (such as: their time, abstention from food, etc.).]

Participants will be asked to dedicate about 14 hours of their time over the course of 8 weeks to participate in this study.

**Benefits:** [Describe anticipated benefits to the individual participants. If test results will be provided, describe and explain procedures to help participants understand the results. If individual participants may not benefit directly, state so here. Do not include compensation or earned course credits in this section.]

Participants may or may not benefit from participating in the study. Benefits that could occur are losing weight through the exercise and lifestyle changes as well as learning about peer mentoring. Through interacting with other participants and the coach, participants may also feel supported in their behavioral change efforts.

[Describe anticipated benefits to society (i.e., added knowledge to the field of study) or a specific class of individuals (i.e., athletes or autistic children).]

Societal benefits include providing evidence to support an intervention delivery modalities that are more conducive to settings like worksites, health plans, and clinics that serve large populations but have limited space, staffing, and resources for traditional in-person interventions.

**Risk/Benefit Analysis:** [Describe the ratio of risks to benefits. Risks to research participants should be justified by the anticipated benefits to the participants or society. Provide your assessment of anticipated risks to participants and steps taken to minimize these risks, balanced against anticipated benefits to the individual or to society.]

The possible risks of the study (including injury during exercise, psychological discomfort completing measures and using the app, and breach of confidentiality) are minimal and are outweighed by the possible benefits to participants (weight loss).

**Economic Considerations:** [Describe any costs to the participants or amount and method of compensation provided. Describe how you arrived at the amount and the plan for compensation; if it will be prorated, please provide the breakdown. Experimental or extra course credit should be considered an economic consideration and included in this section. Indicate when participants will receive compensation.]

Economic burden to subjects includes the time needed for screening, study participation, and follow-up procedures. There is no cost to participants for participating in the study.

Depending on smartphone data usage plan for each participant, usage charges may incur due to increased use of mobile apps.

Participants will be paid in the form of online Amazon gift cards. Participants will receive \$75 for completing the study. Payment will be in the form of an online gift card paid after the follow-up procedures are completed (weigh-in, survey, focus group). The procedures for each assessment will need to be completed before providing compensation.

Additionally, participants may keep the study scale provided to them

Participants who complete the Qualtrics initial screening survey, whether or not they participate in this study, will receive Qualtrics incentives. Their incentives are based on a points system. Respondents accumulate points as they take surveys and then trade in points for E-gift cards to anywhere of their choice (amazon, walmart, target, etc.). The compensation Qualtrics provides is separate from the compensation for participating in the baseline and follow-ups of this trial.

**Data Safety Monitoring:** [This is a prospective plan set up by the study investigators to assure that adverse events occurring during studies are identified, evaluated, and communicated to the IRB in a timely manner. Although the investigators initially propose a Data Safety Monitoring Plan (DSMP), the IRB must approve the plan and may require revision of the plan. A DSMP is required for all human studies at the University of Connecticut except for studies reviewed under the Exempt Criteria. For studies that present more than minimal risk to participants, the IRB will review and determine on a case-by-case basis whether a data safety monitoring board is most appropriate. Please refer to the IRB's policy regarding data safety monitoring *before* completing this section - <http://research.uconn.edu/policies-procedures>.

Issues that should be addressed in the DSMP include the following:

1. Frequency of the monitoring.
2. Who will conduct the monitoring (Under UConn policy a student cannot be the sole person responsible for monitoring the data and safety of the protocol procedures?)
3. What data will be monitored (include compliance with approved IRB protocol?)
4. How the data will be evaluated for problems?
5. What actions will be taken upon the occurrence of specific events or end points?
6. Who will communicate to the IRB and how will communication will occur?
7. Describe procedures to inform the sponsor.

Sample response to issues listed above for minimal risk/ slight increase over minimal risk – “Survey results will be monitored by the PI in conjunction with the student investigator once every two weeks (items 1, 2 and 3). Survey responses will be reviewed to monitor for clarity (i.e., the same question is skipped by 5 or more participants). In that case, the question will be revised and an amendment will be submitted to the IRB (items 4, 5 and 6).”

The Data and Safety Monitoring Plan will include monitoring the study for the progress of recruitment and retention, and the occurrence of adverse events (both serious and otherwise), inclusion/exclusion criteria, adherence to study protocols, and data review (completeness/outliers).

1. Frequency of monitoring

The data report for the 6-week pilot intervention phase will be sent to the two safety officers once follow-ups have been completed. Recruitment is monitored daily during the recruitment phase. All

surveys are monitored once submitted to REDCap within 48 hours. The Facebook group is monitored daily. Weigh-in submissions are monitored weekly. App usage is monitored weekly.

## 2. Safety Monitoring Committee

The two safety officers for this project will include faculty independent from the research team with expertise in clinical psychology, exercise and weight loss interventions, and an understanding of the types and severity of injuries commonly experienced during weight loss trials. The two safety officers will review the reports sent by the project director will use a checklist to document any corrective actions that should be communicated to the principal investigators, the University of Connecticut IRB, and the NIH. In addition, the safety officers may include documentation on whether the principal investigators should provide follow-up to a participant.

## 3. What data will be monitored:

Recruitment rates and adherence to inclusion/exclusion criteria, and ethnic diversity goals: Recruitment progress, including baseline characteristics, will be reviewed. This review will ensure that project deadlines are being met, that participants meet eligibility criteria, and that the ethnic diversity goals outlined in the grant proposal are being met. Recruitment progress is monitored weekly and a final report will be provided in the DSMB report.

### Adherence to study protocols:

Quality control will be conducted in all phases of the project. The Facebook group will be monitored daily for intervention protocol adherence. A final report will be provided in the DSMB report.

### Adverse events:

The adverse event report will include a listing of all adverse events including duration, severity, seriousness, relatedness, action taken, and resolution. Adverse events are documented throughout the intervention and at follow-up. A final AE report will be provided in the DSMB report. In the event of a serious adverse event, the safety officers will be notified immediately.

### Participant retention

Engagement will be tracked during the intervention, and completion of follow-ups will be documented. Participants will be reminded of upcoming study assessments. If a participant chooses to drop from the intervention, they will be given the option to skip the rest of the intervention, but still complete the follow-up. Retention is reviewed and discussed weekly throughout the study and at follow-up. A final retention and engagement report will be provided in the DSMB report.

### Data review (completeness/outliers):

Reports will include completeness of data (visits completed, % of expected forms submitted, % of submitted forms passing edit); missed visits and missing information within visits; descriptive information for each endpoint (change in weight and physical activity) without statistical testing; and quality control analyses for primary outcome (change in weight). Data will be cleaned at the end of each phase (screening, intervention, and follow-up). A final data review reports will be provided in the DSMB report.

## 4. Data evaluated for problems

Data reports will be reviewed by the data manager, program director, statistician, and PI.

## 5. Actions taken during certain occurrences

Baseline participants who report conditions that could create a safety concern while receiving the intervention will be excluded. Adverse events that occur during the intervention will be assessed, recorded, and followed up until resolved. Safety monitoring procedures will be documented in a standard protocol and overseen by the PI and program director. Any adverse events will be immediately reviewed by the program director. The safety officers will be informed of all adverse events during data review. Serious adverse events will be communicated immediately to the PI and safety officers. The NIH and UConn IRB will be notified immediately in the event of serious adverse event. Any death of a study participant will be reported to the NIH and UConn IRB whether or not it appears to be related to the study.

6. IRB Communications

The program director and research coordinator will communicate with the IRB. Communication will occur through emails, phone calls, and/or InfoEd as necessary.

7. Informing sponsor procedures

The sponsor will be notified within 48 hours for serious events that the IRB recommends we report.

**Privacy/Confidentiality Part 1:** [Explain how the privacy interests of participants will be maintained during the study (note that **privacy pertains to the individual not to the data**). Describe how data will be coded. Do not use the any potentially identifiable information such as initials of participants as part of the code. Explain how long data will be kept in an identifiable format and how long de-identified data will be retained. Explain how long the master key or audio or video recordings obtained, will be kept. Consider whether keeping de-identified data will be retained indefinitely and whether participants may be contacted for a follow-up study (explain procedures to retain identifiable contact data is kept.)]

REDCap will be used for data entry and management. The database will be maintained on UConn servers where security will be maintained through access controls. Files will be managed by the data manager and research coordinators, who will control user access and rights. For each user, REDCap will require a REDCap profile, username and password to enter the program. Staff will only have access to the database if the data manager has given them access. UConn IRB and their representatives, and study personnel will have access to the research data, as will the study sponsor if requested. All participants will be assigned an ID number, which will link them to their study data. The ID number will be 2-3 numerical characters representing the number of participants in the study. PHI fields will be stored in a separate REDCap form from other data collection forms. We will provide participant emails to our co-investigator at WPI. We will email the co-investigator a list of participant email addresses. Emails are needed to allow participants access to download the study app onto their phones. Emails will not be attached to the data that participants enter into the app. The participant accounts in the app will be attached to a unique app ID that the UConn staff can link to the REDCap study ID. WPI will not have access to the REDCap study ID, therefore app data will remain unlinked for WPI. Once participants download the app and confirm to the staff that it is downloaded and they can access the app, we will inform WPI to delete the list of email addresses from their records. WebEx recordings will be used to record the audio from the focus groups at the end of the study. The recordings will be maintained on UConn servers where security will be maintained through access controls. We will use Otter.ai transcription software to produce transcripts. Otter.ai retains no ownership rights to the recordings or transcripts. Staff will verify and edit the transcripts and then save the de-identified transcripts to the research drive on the UConn servers and delete the recordings from the drive and the

Otter.ai platform. Please refer to these two sections of the terms of service and privacy policy: Terms of Service; Section 9 and specifically Section 9.3: <https://otter.ai/terms>: In summary, research team retains right to audio recordings and controls how the content is processed, transported, and distributed on the otter.ai platform. Once we delete the recordings from our trash, they are permanently deleted from platform. And from Section 2 of Privacy Policy: <https://blog.otter.ai/privacy-policy/> “We train our proprietary artificial intelligence technology on aggregated, de-identified audio recordings. Only with your explicit permission will we manually review certain audio recordings to further refine our model training data.”. When the recordings are transcribed by study staff (RA’s), the names of the participants are replaced with ID numbers to anonymize the transcript. Data will be completely de-identified once the last assessment is complete. At this time the link between ID number and study data will be destroyed. Study data in the form of hard copies will be stored in a locked file cabinet managed by the program director and will be destroyed 5 years after completion of the study.

Data from ineligible participants, including those excluded for having an exclusionary BMI from the Fitbit scale:

Contact information will be stored in a file with an indication that they are not eligible. However the data collected from the screening, including reason ineligible, will be stored in a separate form and will be de-identified at the end of the study.

If identifiable, sensitive information (illegal drug use, criminal activity, etc.) will be collected, state whether a Certificate of Confidentiality will be obtained.

N/A

Be sure to state whether any limits to confidentiality exist (e.g. mandated reporting) and identify any external agencies (study sponsor, FDA, etc.) that will have access to the data.

Worcester Polytechnic Institute (WPI) will see participant emails and the app use data that is entered into the Habit app. Additionally, study staff from WPI will join the Facebook group to assist participants with any Habit app issues. They all have had CITI training at WPI, will be approved personnel, will not have access to study tracking/survey data, and will not have a link to study ID. Also, it is possible that participants in this study know each other.

If participants will be screened, describe the plans for storage or destruction of identifiable data for those that failed the screening.]

Contact information will be stored in a file with an indication that they are not eligible. However, the data collected from the screening, including reason ineligible, will be stored in a separate form and will be de-identified at the end of the study

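### The ID-to-data link is to be destroyed at the last assessment, yet the only scheduled safety-officer review, which may call for follow-up of a participant, comes at or after that point.

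*Combined protocol and SAP*

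**What the plan says.** Privacy/Confidentiality Part 1 sets the retention rule for enrolled participants: "Data will be completely de-identified once the last assessment is complete". The next sentence reads "At this time the link between ID number and study data will be destroyed". Earlier in that section, the ID number is what connects a person to their study data, and PHI fields are kept in a separate REDCap form.

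The Data Safety Monitoring section sets the safety review:

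- Item 1 (frequency): the data report for the 6-week phase "will be sent to the two safety officers once follow-ups have been completed". No earlier report to the officers is scheduled.
- Item 2 (Safety Monitoring Committee): "the safety officers may include documentation on whether the principal investigators should provide follow-up to a participant".
- Item 3 (Adverse events): "A final AE report will be provided in the DSMB report". For serious events there is a faster route: "In the event of a serious adverse event, the safety officers will be notified immediately".
- Item 5 (actions): "The safety officers will be informed of all adverse events during data review", and also "Adverse events that occur during the intervention will be assessed, recorded, and followed up until resolved".

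Under Design, the Adverse Events paragraph places the formal adverse-event question in the follow-up REDCap survey. The Follow-ups paragraph sends that survey in week 7.

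**The concern.** The confidentiality rule and the safety plan appear to run in the wrong order. The officers may ask that a particular participant be followed up, which needs a route from the record that raised the question to the person. The rule removes that route at a milestone that comes no later than the report. The commitment to follow intervention-period adverse events to resolution has no end tied to the last assessment either, so it can also outlast the link.

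Destruction cannot be undone. If the officers raise a non-serious event that staff are not already tracking by name, a team following the text as written may have no reliable way to find the participant. That would defeat a step the plan itself provides for. The stake is participant safety and traceability; the usability outcomes and planned analyses are untouched.

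**Working it through.** The plan gives no figure to reproduce. The check is on the order of events.

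**Sequence as written**

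| Step | When | Where stated |
|---|---|---|
| Intervention | Weeks 1–6 | Study design |
| Follow-up survey with formal adverse-event question; final weigh-in; focus groups begin | Week 7 onward | Follow-ups; Adverse Events; Focus groups |
| De-identification and destruction of the link | Last assessment complete | Privacy/Confidentiality Part 1 |
| Report sent to safety officers | Follow-ups completed | Data Safety Monitoring, item 1 |
| Officers informed of all adverse events | Data review | Data Safety Monitoring, item 5 |
| Officers may advise follow-up of a participant | After reading the report | Data Safety Monitoring, item 2 |

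**Does the order depend on how the last assessment is read?** The text does not say whether it means each participant's or the study's.

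- If each participant's, links are destroyed one by one, the last of them when the final participant finishes. Follow-ups are complete only then, so every link is gone by the time the report is due.
- If the study's, destruction and the report share one trigger. The officers must still receive the report, read it and respond, so any request comes later.

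Either way, scheduled reports = 1 and reports scheduled before the destruction milestone = 0.

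**Is there a hold elsewhere?** None of the monitoring or confidentiality text delays destruction for the officers' review, for follow-up they request, or for open events. For ineligible people, screening data are de-identified at the end of the study, so a differently worded milestone was in use but was not applied to enrolled participants.

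**How much time does a late-reported event have?** Participant Time gives about 8 weeks in all, including screening, the 6-week intervention and follow-up:

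8 − 6 = about 2 weeks for screening and follow-up together.

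Follow-up alone is therefore planned to take less than about 2 weeks. An event first reported in the week-7 survey has less than that before the planned last assessment, unless a late participant delays the study's last assessment.

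**How many events?** The documents give no adverse-event rate and none is assumed here. The rule reaches the records of all 20 participants; that is its scope, not a count of people harmed.

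**The case against.** The strongest reply is that very little exposure remains in practice. Data Safety Monitoring item 1 has all surveys checked within 48 hours of submission, and item 5 has the program director review any adverse event immediately. During the intervention, events arrive through the counselor or the Facebook group and are passed on within 24 hours, and a weight gain of 5% or more leads to a phone call. Serious events go straight to the officers. With only 20 participants, staff will usually know whom an event concerns. Contact details may also survive in the separate PHI form, the text sets no deadline for the act of destruction, and safety procedures are to be set out in a standard protocol that is not among the documents reviewed.

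Most of this stands, and it is why the point is minor. It makes an untraceable event unlikely, but it does not change the order of events. The officers are independent of the research team, and their review adds most where they ask for follow-up that staff did not start. A surviving contact list does not show whose record prompted the request, and staff memory is not a documented route. A standard protocol might contain a hold, but the text as written does not.

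**Conclusion.** The concern holds. The plan destroys the link at a milestone that is at or before the only scheduled safety-officer report, and nothing in the document keeps it until the review or its consequences are closed. The ordering follows directly from the text under either reading of the last assessment.

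The practical loss is less certain. It requires a non-serious event, first reported late or still open at the end, that the officers want followed up and that staff cannot attribute to a person from other knowledge. It also assumes that the team acts promptly on the destruction rule and that no unseen procedure holds the link. The number of such events cannot be estimated from the documents and is probably small. Severity is minor.

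**What to change.** Replace the two adjacent sentences in Privacy/Confidentiality Part 1 with one that moves the trigger, for example:

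> *De-identification, and destruction of the key tying IDs to study data, will take place only when all of the following are done: the final assessment; the safety officers' review and any participant follow-up it leads to; and resolution or documented closure of every adverse event.*

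The investigators should state what counts as closure, so that one lingering minor event does not hold all 20 records without limit. A narrower alternative is to keep the link after the officers' review only for participants with an open event or an outstanding follow-up request.

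The cost is that data stay identifiable, and the key is held, somewhat longer under the access controls that section already describes. Because this changes a confidentiality commitment in an IRB application, it needs an amendment. The participant information sheet and the Data Security Assessment Form, neither of which is among the documents reviewed, should be checked and aligned if they state a destruction time.
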